7.4 Reporting Procedures

Reporting procedures for all AEs and SAEs are described in **Appendices J and L** (STRONG STAR Adverse Events SOP). The P50 reporting template (included with the SOP Appendix J) will be used to document all AEs and to record their classification and reporting timelines. The severity and research relatedness of AEs and SAEs will be determined by the study PI ([name]) pursuant to the STRONG STAR Adverse Events Adjudication SOP (**Appendix M**).

7.5 Followup for Adverse Events

If an adverse event does not require disenrollment and referral to VA physical or mental health services, then the research team will offer adjunctive services for attrition prevention as outlined in the STRONG STAR ASAP SOP (**Appendix O**). Adjunct services and attrition prevention (ASAP) involves the structured provision of extra adjunctive psychotherapy or medical consultation services designed to mitigate risk of adverse events and maintain participants on protocol (within the limits of good ethics and clinical practice). ASAP sessions can be prompted by the participant, an IE, or an interventionist. These sessions are defined in the SOP as “any out of protocol contact (in person or by telephone) lasting longer than 20 minutes. Each participant is allowed three ASAP sessions during protocol intervention. If more intervention is needed, or the PI believes that a higher level of intervention is needed, then the participant will be dropped from protocol treatment and referred for appropriate intervention in the VA. For participants remaining on protocol with ASAP or referral services, progress will be briefed to the PI daily to monitor progress. When the participant and provider report resolution or stability of symptoms, the participant will be re-assessed with the index measure (e.g., PHQ-9 for depression, NRS for pain) and the results will be discussed with the PI (using only the unique identifier for the participant to maintain blinding) for a final determination of resolution and continuation on protocol.

Please note that STRONG STAR maintains a separate SOP for the monitoring, management, and intervention of suicide risk in study participants (as detailed in **Appendix P**). As detailed in the Suicide Risk SOP, all study staff are thoroughly trained in suicide risk assessment, with formal assessments overseen by a licensed psychologist. This SOP describes specific algorithms for risk level determination and pathways for intervention, follow-up, and implications for research involvement.

7.6 Safety Monitoring

STRONG STAR does maintain a SOP for External Monitoring of all consortium studies (see **Appendix Q**). This has been attached for NCCIH’s information, and safety will be monitored in a manner consistent with standard STRONG STAR practice and will be overseen by the STRONG STAR DSMP.

8. INTERVENTION DISCONTINUATION

There are few reasons for discontinuing any participant from this study. However, under certain circumstances, it may be necessary to buttress study-related treatment to stabilize temporary conditions needing immediate intervention. The STRONG STAR Research Consortium has established an Adjunctive Services and Attrition Prevention (ASAP) policy (see **Appendix O**) describing a preliminary step for intervention in which a distressed participant will be allowed three out-of-protocol intervention sessions (with their individual or group psychotherapist) of 20 minutes or less to stabilize their condition. Should a pre-determined recovery criterion be met (it is impossible to predict all potential emergencies and goals are determined by committee as described in the ASAP SOP), then the participant will remain enrolled in the study. If recovery is not achieved, then the research team (led by the PI) will

decide on whether the participant should be retained. Those requiring a referral for services outside of the study (i.e., if ASAP is not sufficient for symptom management) will be referred to the appropriate services based on the STRONG STAR Suicide Risk SOP (**Appendix P**), through the VA Hospital (i.e., STVHCS), or using the San Antonio area referrals as described on the STRONG STAR Referral Form (**Appendix R1**). All participants referred for services outside of the study protocol will be tracked using the STRONG STAR Referral Form (**Appendix R2**). If a participant needs to be screened for safety when he/she is outside of the immediate San Antonio area, a distance assessment will be completed as described in **Appendix R3**. The following are examples of conditions/circumstances subject to the ASAP process (all of which would qualify as AEs and be tracked/documented accordingly):

1. *Presence of Suicidal Ideation*: If suicidality is identified during the course of study participation, it is vital that this be addressed and stabilized as quickly as possible. Suicide risk will be monitored, classified, and acted-upon based on the STRONG STAR Suicide Risk SOP.
2. *Physical Injury during PT*: If a participant sustains an injury during PT, [name] will collaborate with [name] or [name] to determine if brief ASAP intervention will help restore function and allow continuation of the study protocol.
3. *Exacerbation of PTSD or Depression Symptoms*: In any study involving the treatment PTSD, there is a chance that emotional distress may temporarily worsen. If this happens, adjunctive treatment will be provided using the ASAP protocol.
4. *Opioid Withdrawal Symptoms*: During the course of this study, some participants may choose to stop taking opioid medications (though this is not mandatory), which is increasingly likely in light of recent federal changes to VA prescription practices and the VA's Opioid Safety Initiative. Those who discontinue persistent opioid use may report adverse symptoms of opioid withdrawal that will be monitored at all individual, group, and assessment appointments. Should these symptoms be identified, [name] and/or [name] will be notified. They will meet with the PI to discuss if these symptoms can be reasonably addressed under the ASAP protocol.

Participants will continue to be followed with their permission if study intervention is discontinued. There will be no modifications to the schedule and duration of continued followup if the participant is referred to the VA system for treatment and stabilization (though we will ask permission for frequent checks with the participant on their status to ensure that they are doing well and recovering). They will still be asked to complete all measures at all remaining follow-up intervals.

9. STATISTICAL CONSIDERATIONS

9.1 General Design Issues

Primary Hypothesis: FORT-A participants will demonstrate significantly greater improvements in self-reported than those receiving PRC treatment as usual (TAU).

“Greater improvement” is defined in this study as statistically significant **lower** ODI scores for FORT-A compared to TAU at one-year post-treatment follow-up controlling for differences in ODI at pre-treatment. Logic for selection of ODI as the primary outcome is described in Section 3 of this protocol. Validity and reliability of the ODI has been well-established in over 100 published studies, and use of the ODI will allow comparison of the proposed study results to numerous other pain populations and interventions (allowing for better prediction of result generalizability outside of the population of interest; Fairbank et al., 1980; Fairbank & Pynsent, 2000).

Study Design and Rationale: To test the primary hypothesis, the proposed research needs to simply determine that the experimental intervention (FORT-A) is superior to treatment as usual. The unique requirements of the VA and DoD systems preclude a truly controlled trial (i.e., military and VA IRBs will not approve research denying access to treatment for their covered constituents). Thus, FORT-A cannot be compared to a no-treatment control condition. Because of the variability in chronic pain intervention in the VA system, definition of treatment-as-usual can be difficult. In the original FORT trial, we chose to compare the FORT program to the best available intervention that the DoD had to offer for chronic pain. If FORT was truly an innovative and high-impact intervention, then it should be better than anything else that the military was using to manage chronic pain. Similar logic applies to the present study. FORT-A was developed to improve upon the original FORT program for application to a more complex patient population than that treated in the FORT study. Fortunately, the best available intervention for complex chronic pain in the VA right is through the Polytrauma Rehabilitation Center, making the PRC a natural comparator for this study. Better yet, the PRC is a structured, interdisciplinary program in which all enrolled participants have access to PT services and an interdisciplinary treatment team. If FORT-A is a truly innovative and high-impact intervention, then it should out-perform the PRC (which has openly expressed difficulty in managing chronic pain; Strasser et al., 2008; Clark et al., 2009; Friedemann-Sanchez et al., 2008). Thus, the most parsimonious design for this research is a two-arm, randomized clinical trial comparing 3 weeks of FORT-A to 3 weeks of PRC intervention. After completion of the three week intervention phase, all participants will be permitted to seek additional treatment through the VA system (which is mandated by the VA IRB). We will track treatment engagement through a review of the VA electronic medical record (CPRS, to which all study team members will have access) and interviews with participants at all follow-up assessment intervals.

Secondary Hypothesis: FORT-A participants will demonstrate significantly lower rates of opioid recidivism than TAU participants at one-year post-treatment. Opioid and other pain medication use is being assessed using a timeline follow-back interview and MEMS caps (with the timeline follow-back as the primary measure based on its documented reliability and validity; Sobell & Sobell, 1992).

- ***We are currently discussing the value of adding urine tox screens at pre-treatment, post-treatment, and one-year follow-up.*** The study team previously eschewed the use of a urine tox screen for this research endpoint

because of concerns about the validity and sensitivity of urine tox screens for opioid use. However, in consultation with [name] and the VA Opioid Safety Initiative, we have identified certain tests applied to a urine sample that can reliably and validly illuminate opioid use patterns. We are still examining this addition and how we might be able to partner with the VA to add this to our outcome battery (after discussing this with NCCIH more, of course) without additional cost. The VA system has increased implementation of urine tox screens for opioid using Veterans (see <http://www.veterans.senate.gov/imo/media/doc/VA%20Clancy%20Testimony%203.26.20151.pdf>). However, studies in the PRC population using urine tox screening risk high attrition because Veterans may feel mistrusted. Because timeline followback has shown reliability and validity in the past, we have chosen to stay with this method for tracking opioid use and recidivism to opioid use. However, we will have access to electronic medical records (CPRS) to identify new opioid prescriptions in the VA system and [name] and [name] can access the *Prescription Access in Texas* website (see <https://www.texaspatx.com/Tutorial/Doc/PATIFAQs.pdf>), the Texas State prescription monitoring program, to identify opioid prescriptions dispensed outside of the VA. We are able to keep all opioid medication use confidential as part of the research record and hope that this will increase the reliability and validity of reporting.

Tertiary Hypotheses:

- We plan to use mixed effects hierarchical regression with polynomial change parameters to assess differences in change trajectories for variables related to physical function (functional capacity evaluation, Actiwatch), psychosocial functioning (PHQ-9, PTSD Checklist), and pain variables (Pain Acceptance Questionnaire, Pain Catastrophizing Scale, Pain Intensity Rating). All of these measures were used in the previous FORT study with established reliability and validity.

Exploratory Hypothesis: Based on the PI's ESCAPE trial, we will evaluate the contribution of perceived burdensomeness and pain-related helplessness as potential mediators of the study's primary and secondary endpoints. A subsequent analysis of the ESCAPE data (currently in preparation for publication) has also shown that depression symptoms may mediate these outcomes as well.

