randomized to FORT-A will complete the standardized FORT-A Program (described in detail below). All participants will complete a standardized battery of assessments at pre-treatment (Week 0), post-treatment (Week 4/5), 6-month follow-up (Week 30/31) and 12-month follow-up (Week 56/57; see Figure 1, below).

Interventions and Duration

FORT-A: An amended version of the military Functional Orthopedic Rehabilitation Treatment (FORT) program. For FORT-A, CBT components of FORT were diminished and replaced with mindfulness and Acceptance and Commitment Therapy (ACT) components. Individual FORT treatment sessions have been altered in FORT-A to focus on PTSD symptom management using an abbreviated, manualized Prolonged Exposure treatment. FORT-A includes:

- 12 sessions (90-minutes each) of manualized group pain management
- 12 sessions (90-minutes each) of group-based functional restoration Physical Therapy
- 6 sessions (75 minutes each) of individual psychotherapy for pain and PTSD
- 6 sessions (30 minutes each) of biofeedback for pain management
- Weekly interdisciplinary case staffings

PRC: The STVHCS PRC is the only self-contained PRC in the VA’s nationwide Polytrauma System of Care. The PRC is an interdisciplinary treatment center including: interdisciplinary assessment and treatment, case management, mental health support, physical medicine and rehabilitation (PM&R), physical therapy, speech therapy, prosthetists/orthotists, and other integrated specialty services. The PRC sees approximately 30 new patients each month, most of whom (80%) present with a chronic service-related musculoskeletal pain condition and military trauma comorbidity (traumatic brain injury [TBI], PTSD, depression). Though individual treatment plans may vary, most PRC Veterans will complete up to 12 sessions of Physical Therapy and be followed by a PM&R physician for pain and other symptom management. Pain management with PM&R may include medications, injections, and other palliative medical interventions. The PM&R physicians may also make recommendations about physical function, health behaviors, and mobility.

Sample Size and Population

This research study will include 130 OEF/OIF/OND Veterans who meet the following criteria:

- Present with an ongoing chronic musculoskeletal condition (pain that has been a problem for more than half the days over the past three months) documented in the CPRS record or confirmed by a PM&R physician upon referral to the PRC

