1. STUDY OBJECTIVES

1.1 Primary Objectives

Hypothesis 1: FORT-A will result in significantly greater improvements in pain management among PRC Veterans compared to standard PRC care based on the primary outcome measure of self-report disability (Oswestry Disability Index) at both short- (pre- to post-treatment) and long-term (6/12-month) follow-up.

Hypothesis 2: FORT-A will also result in significant improvements on secondary pain management outcomes compared to PRC, including pain coping (intensity/ cognitions), emotional distress (depression, PTSD, anxiety), and objective disability (functional capacity, gait) at short- and long-term follow-up.

Hypothesis 3: We hypothesize that FORT-A will result in significantly lower rates of opioid recidivism compared to standard PRC treatment based on timeline followback interview at 12-months follow-up.

Hypothesis 4: We also hypothesize that FORT-A will result in significantly less opioid recidivism compared to PRC treatment based on secondary measures of opioid medications including Medication Event Monitoring System (MEMS), pill counts, and consultation with prescribing providers/ documentation in the VA Electronic Health Record (CPRS).

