Based on our previous FORT trial, for which treatment effects in the FORT study arm were maintained at one-year follow-up, it is reasonable to assume that treatment benefits will be maintained after post-treatment and that all post-baseline measures can be averaged for a main effect of treatment. To detect a medium effect with power = 0.80 (based on Cohen’s standardized mean difference $d=0.50$) at $\alpha = 0.05$, we would require $n=50$ in each study arm for a total sample size of $N=100$ for data analysis. Based on our prior FORT research trial and our ongoing VA trials through STRONG STAR, we anticipate less than 30% attrition with a target recruitment goal of $n=65$ in each arm to account for dropouts. Thus the recruitment target for this research is 130 OEF/OIF/OND Veterans with military service-related new onset or exacerbated chronic musculoskeletal pain and persistent opioid use. Both the FORT-A and PRC treatments will be provided on an outpatient basis through the STVHCS PRC (where the PI has several hundred square feet of research space under a VA WOC appointment; see 5.1 and 5.2 in

this document for a more detailed description of the treatment arms). The overall trial will last 5 years (2014-2019). The IRB protocol for this research was approved on July 10, 2014 (see study binder for most current IRB documents and any amendments submitted and approved to the UTHSCSA/VA IRB). Individual participants will be actively enrolled for one year during which time they will:

- Complete pre-treatment assessments
- Undergo a three-week treatment phase
- Complete post-treatment assessment
- Complete 6-month post-treatment follow-up assessments
- Complete 12-month post-treatment follow-up assessments

The following diagram (Figure 2) outlines the administration for this research and the blinding status of individual study personnel/roles:

Figure 2. Study organizational hierarchy

Key:

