9.6 Data Analyses

Data Analysis: To examine our aims and hypotheses we will utilize the generalized linear model, which allows specification of an appropriate distribution for each outcome that can accommodate continuous outcomes (e.g., normal distribution with identity or log link for self-reported disability) and presence/absence outcomes (e.g., binomial with logit link for probability of daily opioid use). We will not stratify our analyses by PTSD or depression, but will account for these variables in our data analysis. Furthermore, we will attend to the influence of missing data on our analyses, and plan on conducting missing values analysis to inform several sensitivity analyses (e.g., LOCF, multiple imputation, etc.) to ensure an intent-to treat principle is observed. Specifically, we will examine the MAR assumption by examining patterns of missingness conditional on baseline assessments, treatment adherence, or other time-varying predictors. Our RCT has one primary endpoint (Oswestry), so both primary and secondary outcomes will be interpreted at a conventional level of statistical significance, $p < 0.05$. To adhere to NIH policy of examining gender and ethnic subgroup analyses, we will add interaction terms (i.e., treatment group x subgroup) for each of our planned analyses. Each analysis is further detailed below:

AIM 1: Assess the efficacy of the FORT-A Program for improved pain management outcomes in (N=130) polymorbid OEF/OIF/OND PRC Veterans with chronic orthopedic pain using a 1:1 randomized clinical trial comparing FORT-A to standard PRC care. To examine our primary hypothesis, we will compare the self-reported disability scores of the two groups at 12-month follow-up while controlling for baseline scores (i.e., an ANCOVA approach). A statistically significant main effect will be interpreted as the groups exhibiting differential change in regards disability. Secondary analyses will use growth curve modeling (mixed effects hierarchical regression with polynomial change parameters) which will model differences in change trajectory over time between the groups across assessment occasions.

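### The polynomial growth models for the secondary outcomes leave degree and time scale open and name no post-treatment contrast; a linear or quadratic trend in weeks would miss most of a short-term effect

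*Combined protocol and SAP*

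**What the plan says.** - **Model.** Under Tertiary Hypotheses, section 9.1 says: "We plan to use mixed effects hierarchical regression with polynomial change parameters to assess differences in change trajectories". It applies this to functional capacity, Actiwatch, PHQ-9, the PTSD Checklist, pain acceptance, catastrophizing and pain intensity. The baseline table in section 6.2.2 marks most of these as Hypothesis 2 endpoints. For the ODI, section 9.6 (Aim 1) says: "Secondary analyses will use growth curve modeling (mixed effects hierarchical regression with polynomial change parameters". No degree and no time coding (weeks, visit number or a transformed scale) is given.
- **Visits.** The synopsis places the assessments at "pre-treatment (Week 0), post-treatment (Week 4/5), 6-month follow-up (Week 30/31) and 12-month follow-up (Week 56/57".
- **Expected effect.** Section 3, drawing on the earlier FORT trial, says that "it is reasonable to assume that treatment benefits will be maintained after post-treatment and that all post-baseline measures can be averaged" into one main effect of treatment.
- **Hypotheses.** In section 1.1, Hypothesis 1 claims an ODI benefit "at both short- (pre- to post-treatment) and long-term (6/12-month) follow-up". Hypothesis 2 claims effects on coping, distress and "objective disability (functional capacity, gait) at short- and long-term follow-up".
- **Primary analysis.** The ODI is compared "at 12-month follow-up while controlling for baseline scores (i.e., an ANCOVA approach" in section 9.6. This is the only ODI comparison tied to a visit.

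**The concern.** The program lasts three weeks. If the arms separate during it and then stay apart, the between-arm difference is a step followed by a plateau. Two of the four visits fall in the first five weeks and the other two roughly half a year apart. On a scale of weeks, a straight line or a parabola has little room to rise between the first two visits and then level off. It moves part of the effect into a fitted baseline difference and spreads the rest over the year.

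The short-term claims of Hypotheses 1 and 2 have no other named analysis. Section 9.6 interprets secondary outcomes at p < 0.05, so a real post-treatment benefit could be reported as small or absent. Because the degree is not fixed, the result could also depend on a choice made after the data are seen.

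**Working it through.** **Inputs.** From the documents: 65 per arm, two-sided alpha 0.05, d = 0.50, SD 6.6 and 3.3 ODI points (section 9.2); visits at weeks 0, 4.5, 30 and 56 (synopsis, taking the midpoint of week 4/5). The effect profile (0, 1, 1, 1) puts section 3's maintenance assumption into numbers. The documents give no correlation between visits, so equal correlations of 0.5 and 0.7 are assumed.

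**The plan's own figure.** 0.50 × √(65/2) = 2.85, and the normal approximation gives power 0.81 (t-test 0.81), against the stated 0.80. This confirms the scale used here but does not bear on the polynomial models.

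**Linear trend in weeks.** Mean week = (0 + 4.5 + 30 + 56)/4 = 22.625. Sum of squares about it = 2008.7. Cross-product with (0, 1, 1, 1) = 22.625. Slope = 22.625/2008.7 = 0.01126 per week. Fitted change from baseline:
- week 4.5: 4.5 × 0.01126 = 0.05
- week 30: 0.34
- week 56: 0.63

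**Quadratic in weeks.** The least-squares fit at the four visits is 0.358, 0.542, 1.136 and 0.964, so the changes from fitted baseline are 0.18, 0.78 and 0.61.

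Share of a true step recovered, as change from the fitted baseline:

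| Time model | Post-treatment | 6 months | 12 months |
|---|---|---|---|
| Linear, weeks | 5% | 34% | 63% |
| Quadratic, weeks | 18% | 78% | 61% |
| Linear, visit number | 30% | 60% | 90% |
| Quadratic, visit number | 80% | 110% | 90% |
| Linear, log(1 + week) | 39% | 79% | 93% |
| Quadratic, log(1 + week) | 94% | 108% | 93% |
| Cubic, or visit as a category | 100% | 100% | 100% |

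For a true 3.3-point difference, the post-treatment effect would read as 0.05 × 3.3 = 0.2 points (linear in weeks) or 0.18 × 3.3 = 0.6 points (quadratic). The 12-month change would read as about 2.1 or 2.0 points.

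**Sensitivity of the shares.**
- Random-intercept and random-slope covariances give the same fits with complete data.
- Placing post-treatment at week 4 or week 5 gives 4-6% (linear) and 16-21% (quadratic).
- Allowing no arm difference at baseline (correlation 0.5) gives 7% and 22% at post-treatment, and 84% and 74% at 12 months.

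**Power of the joint group-by-time test.** With equal correlation ρ, the noncentrality is λ = [n / (2(1 − ρ))] × d² × SS. SS is the sum of squares of the fitted profile about its mean. The multiplier is 65/1.0 × 0.25 = 16.25 at ρ = 0.5 and 65/0.6 × 0.25 = 27.08 at ρ = 0.7.

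| Model | df | SS | λ (0.5 / 0.7) | Power (0.5 / 0.7) |
|---|---|---|---|---|
| Linear, weeks | 1 | 0.255 | 4.14 / 6.90 | 0.53 / 0.75 |
| Quadratic, weeks | 2 | 0.392 | 6.37 / 10.6 | 0.61 / 0.84 |
| Visit as a category | 3 | 0.750 | 12.2 / 20.3 | 0.85 / 0.98 |

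With visit as a category, the post-treatment change contrast has SE √(2/65 × 2(1 − ρ)) = 0.175 or 0.136 SD. That gives z = 2.85 or 3.68, and power 0.81 or 0.96.

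If 30% attrition leaves 46 per arm (65 × 0.7 = 45.5), the ordering is unchanged: linear 0.40 / 0.60, quadratic 0.46 / 0.69, visit as a category 0.69 / 0.90.

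**A different effect shape.** For a gradually building difference (0, 0.5, 0.75, 1), the same formula gives SS 0.443 (linear) and 0.547 (by visit). Power is then 0.77 / 0.93 for the linear trend in weeks and 0.71 / 0.91 by visit.

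**The case against.** The strongest reply is that the plan never commits to a line or a parabola in weeks. With four visits an arm-specific cubic is saturated and reproduces any profile. A quadratic in visit number or log time recovers 80% or 94% at post-treatment, and its joint-test power (0.86 / 0.98 and 0.88 / 0.98) is no lower than that of visit as a category. A reader might infer that polynomial models cannot follow the expected effect, or that short-term effects will be smoothed away. The documents support neither, because both readings need a degree and a time scale that the plan does not state.

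It can also be said that the maintenance assumption in section 3 is a sample-size argument and is not a prediction for every secondary outcome. Section 5.1 itself warns that PTSD symptoms may worsen in the first week of exposure treatment. If the effect builds gradually, the linear model has slightly more power. Growth curves are a conventional choice when the stated aim is to compare trajectories, and section 9.1 places these outcomes under tertiary hypotheses.

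All of this stands, and it makes the figures conditional. It does not supply what is missing. The wording permits the low-order choices in weeks as readily as the harmless ones. For the same step effect, the post-treatment estimate could be anywhere from 5% to 100% of the truth. Nor do polynomial coefficients by themselves give the differences at post-treatment, 6 and 12 months that section 1.1 hypothesizes.

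**Conclusion.** The point holds as one of under-specification in non-primary analyses. Degree, time scale and the post-treatment contrast are all missing, while two hypotheses claim a short-term effect.

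If a linear or quadratic trend in weeks were used and the effect were maintained as section 3 expects, about 80-95% of the post-treatment effect would be lost. Nearly 40% of the 12-month change would be lost too, or 16-26% if no baseline arm difference is allowed. Group-by-time power would fall from 0.85-0.98 to 0.53-0.75 (linear) or 0.61-0.84 (quadratic). The power figures rest on d = 0.50, 65 per arm, complete data and an assumed equal visit correlation of 0.5-0.7. With complete data and a freely fitted baseline difference, the recovered shares are the same under the equal-correlation, random-intercept and random-slope covariances tried.

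A reader might also infer that the main ODI result is at risk. It is not: the baseline-adjusted comparison at 12 months uses no time trend.

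**What to change.** In section 9.1 (Tertiary Hypotheses) and section 9.6 (Aim 1 secondary analysis), make the model one with visit as a category: arm-by-visit terms, baseline adjustment and an unstructured covariance. Name the arm contrasts at post-treatment, 6 months and 12 months as the estimates that answer the short- and long-term parts of Hypotheses 1 and 2. Polynomial growth curves may stay as a supplementary description, with degree and time scale fixed in advance.

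This changes the analysis text only; no visits, data or participants are added. The cost is a few more parameters per model and slightly less power if the true effect is near linear in time (0.71 / 0.91 against 0.77 / 0.93 in the gradual example).
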